7 PROGRAMMING SPECIFICATIONS

The rules for programming derivations and dataset specifications are provided in separate documents.

The following sample SAS statement provides the framework for the MI method:

CONVERT DATASET INTO MONOTONE MISSING DATA PATTERN (IMPUTING ARBITRARY MISSING DATA):

```
PROC MI data=<dataset> nimpute=30 seed=2006 out=<dataset1>;
  VAR age BMI baseline... visit1-visit8;
  MCMC chain=multiple nbiter=500 niter=300 impute=monotone;
  BY treatment;
RUN;
```

IMPUTE MISSING VALUES:

```
PROC MI data=<dataset1> nimpute=1 seed=2006 out=<dataset2>;
  CLASS treatment sex race region;
  MONOTONE regression (/details);
  MNAR model (visit2-visit8/ modelobs=CCMV);
  VAR treatment age sex race region BMI baseline....;
  BY _imputation_;
RUN;
```

PERFORMING MMRM:

```
PROC MIXED data=<dataset2>;
  CLASS subject treatment agegrp visit;
  MODEL value=treatment agegrp region visit visit*treatment / ddfm=kr;
  REPEAT visit/sub=subject type=UN;
  LSMEANS visit*treatment/DIFF CL;

  BY _imputation_;
  ODS output estimates=<dataset3>;
RUN;
```

COMBINE RESULTS:

```
PROC MIANALYZE data=<dataset3>;
  MODELEFFECTS estimate;
  STDERR stderr;
RUN;
```

VARIABLE ORDER TO BE USED IN THE PROC MI PROCEDURES:**To Create Monotone Missing Data Pattern**

- sSOL: age, baseline BMI, baseline ISI, baseline log(mean sSOL), log(mean sSOL) at first 7 nights, log(mean sSOL) at Month 1, log(mean sSOL) at Month 2, log(mean sSOL) at Month 3, log(mean sSOL) at Month 4, log(mean sSOL) at Month 5, log(mean sSOL) at Month 6

- sSE: age, baseline BMI, baseline ISI, baseline mean sSE, mean sSE at first 7 nights, mean sSE at Month 1, mean sSE at Month 2, mean sSE at Month 3, mean sSE at Month 4, mean sSE at Month 5, mean sSE at Month 6
- sWASO: age, baseline BMI, baseline ISI, baseline mean sWASO, mean sWASO at first 7 nights, mean sWASO at Month 1, mean sWASO at Month 2, mean sWASO at Month 3, mean sWASO at Month 4, mean sWASO at Month 5, mean sWASO at Month 6
- sTST: age, baseline BMI, baseline ISI, baseline mean sTST, mean sTST at first 7 nights, mean sTST at Month 1, mean sTST at Month 2, mean sTST at Month 3, mean sTST at Month 4, mean sTST at Month 5, mean sTST at Month 6

To Impute Missing Values

- sSOL: treatment, sex, race, region + variables used to create monotone missing data pattern
- sSE: treatment, sex, race, region + variables used to create monotone missing data pattern
- sWASO: treatment, sex, race, region + variables used to create monotone missing data pattern
- sTST: treatment, sex, race, region + variables used to create monotone missing data pattern

TIPPING POINT SENSITIVITY ANALYSIS:

The following sample SAS statements and algorithm provide the framework for the Tipping Point Sensitivity Analysis:

A tipping point sensitivity analysis will be conducted on the endpoints sSOL (Log sSOL), sSE and sWASO using the multiple imputation methodology as described in the section above but with the following modifications:

1. Convert the dataset into monotone missing data patterns (30 datasets), as above.
2. Generate the dataset so that there is a missing data indicator for data that has been imputed (ie, 1= observed, 0= missing).
3. Perform CCMV imputation. Ensure the missing data indicator is kept in this dataset.
4. Using the CCMV dataset, the second MI procedure (monotone missing values) is to be modified to introduce an adjustable shift (i.e sensitivity parameter) to the imputed values for only the treatment groups LEM10 and LEM5, corresponding to a MNAR/CCMV assumption when the shift is zero. These shifts are to be applied to Month 6 only.
5. For each shift apply the PROC MIXED model by `_imputation_` and combine results using PROC MIANALYZE
6. Store results from PROC MIANALYZE for each shift
7. If the MNAR (shift=0) model has a p-value that is significant (<0.05), then the `<shift>` value will be systematically incremented until the resulting p-value is ≥ 0.05 .

8. Step 2 may be repeated iteratively starting with the shift found just prior to p-value >0.05 ending with the p-value ≥0.05 found in Step 2, using smaller increments, until a shift is found where the rounded p-value has a value of 0.05 to a reasonable accuracy.
9. The values for <shift> in Step 1 will be applied uniformly (same shift) to both LEM5 and LEM10 at Month 6.
10. The values for <shift> will correspond to worsening values for the endpoint according to the following:
 - Increasing positive shift values (sSOL, sWASO)
 - Increasing negative shift values (sSE)
11. The following specifies which comparisons are of interest when evaluating p-values for this procedure:
LEM5 and LEM10 vs. Placebo (sSOL, sSE, sWASO)

For the MAR sensitivity analysis, the following procedure should be applied:

1. Convert the dataset into monotone missing data patterns (30 datasets), as above.
2. The second MI procedure (monotone missing values) is to be modified to introduce an adjustable shift (i.e sensitivity parameter) to the imputed values for only the treatment groups LEM10 and LEM5, corresponding to a MAR assumption when the shift is zero. These shifts are to be applied to Month 6 only.

```

PROC MI data=<dataset1> nimpute=1 seed=2006 out=<dataset2>;
  CLASS treatment sex race region;
  MONOTONE regression ( /details);
  MNAR adjust (visit8/ shift=<shift> adjustobs=(treatment=LEM5));
  MNAR adjust (visit8/ shift=<shift> adjustobs=(treatment= LEM10));
  VAR treatment age sex race region BMI baseline...visit8;
  BY _imputation_;
RUN;

```

3. If the MAR (shift=0) model has a p-value that is significant (<0.05), then the <shift> value will be systematically incremented until the resulting p-value is ≥0.05.
4. Step 2 may be repeated iteratively starting with the shift found just prior to p-value >0.05 ending with the p-value ≥0.05 found in Step 2, using smaller increments, until a shift is found where the rounded p-value has a value of 0.05 to a reasonable accuracy.
5. The values for <shift> in Step 1 will be applied uniformly (same shift) to both LEM5 and LEM10 at Month 6.
6. The values for <shift> will correspond to worsening values for the endpoint according to the following:
 - Increasing positive shift values (sSOL, sWASO)
 - Increasing negative shift values (sSE)

7. The following specifies which comparisons are of interest when evaluating p-values for this procedure:

- LEM5 and LEM10 vs. Placebo (sSOL, sSE, sWASO)

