3.3.5 Handling of Missing Data, Dropouts, and Outliers

This study collected sleep diary data directly from subjects via a vendor-provided hand-held device; it is possible that some values entered by subjects may have resulted from input errors. For example, it is not possible for a total waketime to be longer than the time the subject spends in bed for the night. In such cases, erroneous data will be considered as missing values in data analyses. Efficacy data handling will be mentioned in the [Section 6.1](#).

The primary and key secondary efficacy endpoints will be analyzed using mixed effect model repeated measurement analysis (MMRM), the missing values will be imputed using pattern-mixture multiple imputation (MI) assuming the missing data is missing not at random (MNAR) utilizing the complete case missing value pattern (CCMV). Additional sensitivity analyses will also be performed on primary and key secondary efficacy endpoints as follows:

Table 3 Multiple Imputation Methods

MI Methods	Assumption	Analysis Type																																																																
Complete Case Missing Value (CCMV)	Subjects with missing data at any day have a similar distribution as the completers within the respective treatment group (Pattern 1, below), where completers are defined as having no missing assessments for any post-baseline visits	Primary																																																																

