3.3.6 Other Considerations

The following estimands are evaluated for the primary efficacy endpoint (change from baseline in mean sSOL on Month 6) in this study ([Mallinckrodt, et al., 2012](#), and [ICH, E9\(R1\) Final Concept Paper, 2014](#)). The details of the analysis method are discussed in [Section 3.4](#).

Table 4 Estimands

Estimand	Description	Population	Intervention Effect of Interest	Analysis Type
Difference in outcome improvement for all randomized subjects	- all randomized subjects regardless of the treatment subjects actually received - include data after dropout	FAS	missing values imputed using MI assuming MNAR utilizing CCMV missing value pattern (complete cases) (Assumes the probability of missing observations for any subject depends on the unobserved events. For the missing pattern, complete cases will be used in the imputation. Thus this method assumes dropouts or subjects with missing values have similar treatment effect as the completers within the respective treatment group.)	primary
Difference in outcome improvement for all randomized subjects	- all randomized subjects regardless of what treatment subjects actually received - include data after dropout	FAS	missing values imputed using MI assuming MNAR utilizing CCMV-7 missing value pattern (all available up to 7 monotone missing patterns) (Assumes the probability of missing observations for any subject depends on the unobserved events. For the missing pattern, complete cases up to 7 monotone missing patterns will be used in the imputation – see Section 3.4.1.3 for details. Thus this method relaxes the assumption of the primary analysis of using only completers to impute the missing data.)	Sensitivity (CCMV-7)
Difference in outcome improvement for all randomized subjects	- all randomized subjects regardless of what treatment subjects actually received - include data after dropout	FAS	a range of shifts starting from the primary analysis (CCMV) will be used in the multiple imputation of missing data assuming MNAR to identify the specific shift and treatment effect that will tip the results from statistically significant to non-significant	Sensitivity (tipping point)

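### The SAP's CCMV imputation code shares slopes and residual variance across the three arms, while Tables 3 and 4 promise imputation from completers within each arm; the Month 6 contrasts move if slopes differ by arm and dropouts also differ from their arm's completers

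*SAP*

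**What the plan says.** SAP 3.3.5, Table 3, describes the primary method (complete-case missing value, CCMV) as treating subjects with missing data as distributed like "completers within the respective treatment group". SAP 3.3.6, Table 4, says much the same for the primary estimand: "dropouts or subjects with missing values have similar treatment effect as the completers within the respective treatment group".

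SAP Section 7 then gives two PROC MI steps. The first makes the missing pattern monotone and is run `BY treatment`. The second performs the CCMV imputation. It has "CLASS treatment sex race region", a variable list that opens "VAR treatment age sex race region BMI baseline", a regression written as "MONOTONE regression (/details" with no effects named, and donors set by "MNAR model (visit2-visit8/ modelobs=CCMV". Its only BY variable is `_imputation_`. The variable-order list in the same section agrees with the code: "sSOL: treatment, sex, race, region + variables used to create monotone missing data pattern". The entries for sSE, sWASO and sTST are built the same way.

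The body text is different again. SAP 3.4.1.1 (sSOL) and 3.4.2.1 (sSE and sWASO) list the imputation predictors with no treatment term. For the SAS statements, 3.4.1.1 sends the reader to Section 7.

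**The concern.** The SAP contains three descriptions of one imputation model: within-arm donors (Tables 3 and 4), one regression with a treatment main effect (Section 7), and a predictor list without treatment (3.4.1.1 and 3.4.2.1). Nothing reconciles them.

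The step at issue matters because Month 6 is last in the variable order. The monotone-conversion step fills only gaps that precede an observed value, so it never fills a missing Month 6 value. Every imputed Month 6 value therefore comes from the second step, and these values feed all six tests in the gate-keeping sequence of SAP 3.3.3. If a dropout's earlier diary values are worse than those of completers in the same arm, a slope borrowed partly from other arms changes that subject's imputed Month 6 value.

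The planned sensitivity analyses would not show the effect. CCMV-7 (3.4.1.3 and 3.4.2.2) specifies no by-arm step, the CCMV tipping point modifies the same second step, and the MAR tipping-point code is again run by `_imputation_` only.

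**Working it through.** **What the code fits.** The reading of the unlisted regression effects as main effects of the preceding variables is taken from the form of the code. On that reading the second step gives arm-specific intercepts, common slopes on baseline and earlier visits, and one residual variance. Within-arm imputation would allow all three to differ by arm.

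**The plan's own figure.** SAP Section 2 has sSOL difference −8.7 min, SD 33 min, two-sided 0.05, 90% power. n = 2 × (1.960 + 1.282)² × 33² / 8.7² ≈ 303 per arm, and power at 300 per arm is 89.8%. This reproduces the stated 300 within rounding. The SAP gives no figure for the imputation effect, so there is none to reproduce.

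**Formula (one step, from the last observed visit to Month 6).** Let π be the fraction missing at Month 6, b the slope of Month 6 on the earlier value, and δ the dropout-minus-completer mean of that earlier value. Take three equal arms, equal π, and both drug arms with slope b_D. The pooled slope is (2b_D + b_P)/3.
- Drug arm, pooled minus within-arm: π × (b_P − b_D)/3 × δ_D.
- Placebo arm, pooled minus within-arm: −π × 2(b_P − b_D)/3 × δ_P.
- Contrast (drug − placebo): π × (b_P − b_D) × (δ_D/3 + 2δ_P/3).

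The shift is zero if the slopes are equal, if both δ are zero, or if δ_D = −2δ_P.

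**Numbers.** π, the slopes and δ are assumptions, because the documents give none of them. Ranges used: π 0.1 to 0.5, slope gap 0.1 to 0.3, δ 0 to 1 SD and the same in all arms, SD 33 min.
- π 0.2, gap 0.2, δ 0.5 SD: 0.2 × 0.2 × 0.5 × 33 = 0.66 min.
- π 0.5, gap 0.2, δ 0.5 SD: 0.5 × 0.2 × 0.5 × 33 = 1.65 min.
- π 0.5, gap 0.3, δ 1 SD (extreme corner): 4.95 min.

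With SE = 33 × √(2/300) = 2.69 min, 0.66 min is 0.66/2.69 ≈ 0.25 SE. A 0.66 min shift on −8.7 takes power at 300 per arm from 89.8% to 84.7% if toward the null, or to 93.5% if away from it.

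**Simulation.** Sequential complete-case multiple imputation over baseline and seven visits, 4,000 per arm, 40 replicates, 5 imputations, Month 6 ANCOVA. Entries are the pooled contrast minus the by-arm contrast, in minutes; Monte Carlo SE is 0.03 to 0.10.

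| Scenario | 20% missing | 50% missing |
|---|---|---|
| Equal slopes, dropouts 0.5 SD worse | 0.03 | −0.03 |
| Slopes 0.9 placebo, 0.7 drug; dropouts like completers | 0.00 | −0.03 |
| Same unequal slopes; dropouts 0.5 SD worse | +0.89 | +2.11 |
| Same unequal slopes; dropouts 1 SD worse | +1.74 | +4.31 |
| Equal slopes, unequal residual variance (so unequal correlations); dropouts 0.5 SD worse | 0.04 | −0.06 |

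The simulation chains the regression over several visits and the formula covers one step, so close agreement is not expected. Both show that unequal slopes and a dropout–completer difference are needed together. The second and last rows have unequal correlations and no shift. The positive shifts are toward the null because placebo was given the steeper slope and dropouts the worse values. By the formula, reversing the slope gap reverses the sign.

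**The case against.** A reader might infer that the contrast is shifted whenever visit-to-visit correlation differs between drug and placebo. It is not: two of the simulated scenarios have different correlations and no shift. A reader might also infer that the imputation ignores treatment. It does not: the main effect gives each arm its own intercept, and Table 4's wording about a similar treatment effect could be read as met by that term. Table 3's wording, which speaks of a similar distribution, cannot.

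Other points on the plan's side carry some weight:
- The primary MMRM uses one unstructured covariance matrix for all arms, and the sample size uses one SD, so shared slopes fit the plan's general modelling. That is an assumption of the same kind, not evidence for it.
- The code is labelled a sample and is visibly skeletal: its PROC MIXED omits the baseline covariate that 3.4.1 requires. But 3.4.1.1 relies on Section 7 for the implementation, and the prose variable order also names treatment, so this is not a typing slip.
- The MMRM under MAR and the completer analysis (3.4.1.4 and 3.4.2.3) impute nothing and so bypass this step. The MAR model still shares its covariance across arms, so it is not a check on the within-arm assumption.
- The 50% discontinuation figure in SAP Section 2 is a safety-exposure worst case, and data retrieved after discontinuation are used, so Month 6 missingness may be well below it.

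These points limit the likely size. They do not make the code match Tables 3 and 4.

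**Conclusion.** The inconsistency is real and sits in the primary and both key secondary analyses. As written, Section 7 does not implement the within-arm completer assumption that the SAP states.

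The effect on the Month 6 contrasts is conditional. It needs regression slopes on earlier visits that differ by arm and dropouts whose earlier values differ from those of their own arm's completers, without the arm effects cancelling. Neither size nor direction can be derived from the documents, so they do not support a claim that the primary result is biased, or biased in a given direction. Illustratively, on a 33-minute SD scale with a slope gap of 0.2 and dropouts 0.5 SD worse, the shift is about 0.7 to 0.9 min at 20% missing and about 2 min at 50% missing. It is zero if slopes are equal or dropouts resemble completers.

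The primary sSOL analysis is on the log scale, so minutes serve only as a yardstick. In SD units the 0.66 min case is 0.2 × 0.2 × 0.5 = 0.02 SD.

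**What to change.** Settle this before treatment is unblinded; a later switch would be a data-dependent choice on the primary endpoint.

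1. Run the second PROC MI `BY _imputation_ treatment` (data sorted accordingly), and remove treatment from its CLASS and VAR statements and from the variable-order lists. Do this for sSOL, sSE and sWASO, and for sTST wherever it is imputed. Alternatively, keep one run and add treatment-by-prior-value terms; this frees the slopes but still shares the residual variance.
2. Bring 3.4.1.1 and 3.4.2.1 into line with the choice. If common slopes are what the sponsor wants, Tables 3 and 4 must say so instead.
3. In the CCMV and MAR tipping-point runs, add the Month 6 shift in a data step to flagged imputed LEM5 and LEM10 values. The CCMV procedure already keeps a missing-data indicator; the MAR procedure needs one, because its present code selects on treatment inside PROC MI. Month 6 is the last variable imputed, so adding the shift afterwards affects no other imputed value.

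The cost is modest, but it is more than a one-line edit. Each regression would use one arm's completers only, for example 300 × 0.8 = 240 at 20% missing or 300 × 0.5 = 150 at 50%, so imputations are slightly noisier.

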3.4.1.1 Multiple Imputation

Step 1 (imputing missing data): Thirty multiple imputed complete datasets were to be constructed using imputation regression model of baseline sSOL, baseline ISI, age, sex, race (white, black, and other), and region (North America, Europe and New Zealand, Asia), baseline BMI, baseline log(sSOL), baseline ISI with a predefined arbitrary seed number (seed=2006). SAS PROC MI will be used to implement the imputation procedure using all available values. The dataset will be converted into monotone missing pattern by imputing arbitrary missing data as the first step. The monotone data will then be imputed with monotone regression method and MNAR. The sample SAS statement can be found in [Section 7](#).

Step 2 (performing MMRM using each imputed dataset): The MMRM model with factors of age group (<65 years old, ≥65 years old), region (North America, Europe and New Zealand, Asia), treatment, visit (1st 7 nights, Month 1, Month 2, Month 3, Month 4, month 5 and Month 6), and treatment-by-visit interaction as fixed effect, and the baseline log(sSOL) as a covariate will be applied to each imputed dataset. SAS PROC MIXED will be used for the MMRM analysis. The sample SAS statement can be found in [Section 7](#).

Step 3 (combine results): Resulting treatment effect parameter estimators and standard errors from each of 30 multiple imputed datasets from Step 2 will be combined using SAS PROC MIANALYZE to obtain the pooled treatment effect and variance parameter estimators according to Rubin's rules ([Rubin DB, 1987](#)). The sample SAS statement can be found in [Section 7](#).

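### The sample PROC MIXED code in SAP Section 7 does not match the stated primary model: no baseline covariate, region not classed, response undefined, and no output table to pool

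*SAP*

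**What the plan says.** **The text.** SAP 3.3.2 lists baseline, region and age group as covariates for the primary and secondary analyses. SAP 3.4.1 analyses the change in sSOL from Study Baseline, log-transformed, adjusted for the Study Baseline value, region (three named levels), age group, treatment, time and treatment by time. Protocol 9.7.1.6.1 also adjusts for baseline and region. In Step 2 of SAP 3.4.1.1 the model has these fixed effects "and the baseline log(sSOL) as a covariate will be applied to each imputed dataset". SAP 3.4.2.1 states the same structure for sSE and sWASO, each with its own baseline.

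**The code.** Each of the three steps in SAP 3.4.1.1 sends the reader to Section 7 for sample statements. There PROC MIXED has "CLASS subject treatment agegrp visit" and "MODEL value=treatment agegrp region visit visit*treatment / ddfm=kr". Treatment comparisons are requested only through "LSMEANS visit*treatment/DIFF CL". The results are saved with "ODS output estimates=<dataset3>", and PROC MIANALYZE reads that dataset. The imputation step just above does class region: "CLASS treatment sex race region".

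**Where the code is reused.** SAP 3.4.2.1 applies the same three steps to sSE and sWASO. The tipping-point algorithm in Section 7 reapplies the PROC MIXED model at every shift.

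**The concern.** Text and code describe different models for the six comparisons in the gate-keeping sequence (SAP 3.3.3) and for their tipping-point analyses. The PROC MI `VAR` lines mark omitted variables with an ellipsis. The `MODEL` line has no ellipsis or placeholder, so it reads as complete.

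A programmer who repaired the output request but otherwise kept the printed model would leave out the baseline adjustment that the text requires. Between-subject baseline variation would stay in the error term and chance baseline imbalance would go uncorrected. The p-value would differ from that of a programmer who followed the text.

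**Working it through.** **1. Text against code**

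| Element | SAP text | Section 7 code |
|---|---|---|
| Baseline | covariate, log(sSOL) for the primary | absent |
| Region | three named levels | in MODEL, not in CLASS |
| Response | change from Study Baseline, log scale for sSOL | `value`, undefined; the imputed variables listed are visit levels |
| Comparison | contrasts at Month 6 | all visit-by-treatment differences |
| Table to pool | pooled treatment effect | `estimates`, with no ESTIMATE statement |

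Renaming the output table would not be enough. Three arms by 7 visits give 21 cells and 21 x 20 / 2 = 210 pairwise differences per imputation. Two of these are needed for each endpoint, and nothing in the code selects them.

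**2. The plan's own figure**

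Inputs from SAP Section 2: difference -8.7 min, SD of change 33 min, 300 per arm, two-sided 0.05.

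SE = 33 x sqrt(2/300) = 2.694. Power = Phi(8.7/2.694 - 1.96) = Phi(1.269) = 89.8%, which agrees with the stated 90% to within rounding. The per-group sizes in SAP Table 2 also reproduce closely (for example 303 against 300 for this row).

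**3. Cost of leaving baseline out, with change as the response**

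Assume equal SD s at baseline and Month 6, and correlation r between them. The documents give no r, so a range is shown.

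- Variance of the unadjusted change: 2s²(1 - r)
- Residual variance after baseline adjustment: s²(1 - r²)
- Ratio: 2/(1 + r)

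Taking 33 as the unadjusted SD of change, the adjusted SD is 33 x sqrt((1 + r)/2).

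| r | Variance ratio | SE increase | 300 per arm acts like | Power without baseline | Power with baseline |
|---|---|---|---|---|---|
| 0.3 | 1.54 | 24% | 195 | 89.8% | 98.0% |
| 0.5 | 1.33 | 15% | 225 | 89.8% | 96.2% |
| 0.7 | 1.18 | 8% | 255 | 89.8% | 93.8% |
| 0.8 | 1.11 | 5% | 270 | 89.8% | 92.6% |

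Example at r = 0.5: adjusted SD = 33 x sqrt(0.75) = 28.6; SE = 2.333; power = Phi(8.7/2.333 - 1.96) = 96.2%.

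**4. Simulation check**

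Complete data at Month 6, 900 subjects in three arms, 2,000 replicates, true effect -0.2 SD. At r = 0.5 the mean SE was 0.0708 with baseline and 0.0817 without, a ratio of 1.15. Mean estimates were -0.199 and -0.201, so there was no bias. Entering region as one linear term, under an assumed non-linear region effect of 0.3 SD, raised the SE by about 1% (0.0817 to 0.0825 without baseline).

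**The case against.** The best defence is that Section 7 offers the code as a sample and a framework, while the text states the model correctly in several places. The block cannot run as printed anyway: it has dataset placeholders, writes `REPEAT` for `REPEATED`, and saves a table that is never made. Someone must repair it, and the text they would consult names baseline. This stands. It makes the point a conflict between text and code, not evidence that the wrong model would be run.

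Two further replies also stand. The planned 90% power uses the SD of change with no credit for adjustment, so with change as the response the omission forfeits a gain and does not push power below plan. Region outside CLASS matters little: numeric coding gives one slope, and text coding stops the run.

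A reader might infer more in two places.

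- **A much larger loss.** If `value` were the raw post-baseline level, the SE factor would be 1/sqrt(1 - r²): 40% at r = 0.7, with power 71% against 94%. The code does not define `value`, but SAP 3.4.1 analyses change from Study Baseline, so these figures do not measure the cost under the stated analysis.
- **An imputation step that contradicts Table 3.** SAP 3.3.5 likens subjects with missing data to "completers within the respective treatment group", while the second PROC MI step is run by imputation number and has "VAR treatment age sex race region BMI baseline" plus further terms. Treatment is in both CLASS and VAR there, and the variable lists in Section 7 name it as an imputation variable, so imputed means are arm-specific. Table 3 summarises an assumption and does not require arm-specific slopes. Replacing the BY variable with treatment would also pool the 30 imputed datasets into one regression.

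**Conclusion.** The PROC MIXED block is wrong as written and conflicts with SAP 3.3.2, 3.4.1, 3.4.1.1 and 3.4.2.1. Taken literally it yields no pooled result. The loss of precision arises only if the output request is repaired and baseline is still left out: SE up by about 5% to 24%, and power 89.8% against 92.6% to 98.0%, for r from 0.8 to 0.3.

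These sizes rest on an assumed correlation, equal SDs at baseline and Month 6, complete data, 33 minutes read as the unadjusted SD of change, and the minutes scale, whereas the primary analysis is on log(sSOL). If 33 were the residual SD after adjustment, power without baseline would be 74% to 86.5% for r from 0.3 to 0.8. The SAP describes it as the SD of change, so that reading is not adopted. Randomization keeps the estimate unbiased, and type I error is not inflated.

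**What to change.** In Section 7:

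- Define `value` as the change from Study Baseline, on the log scale for sSOL.
- Use `CLASS subject treatment agegrp region visit;`
- Use `MODEL value = baseline treatment agegrp region visit treatment*visit / ddfm=kr;` where `baseline` is baseline log(sSOL) for sSOL and the corresponding baseline value for sSE and sWASO.
- Use `REPEATED visit / subject=subject type=un;`
- Pass only the Month 6 LEM10-PBO and LEM5-PBO differences to PROC MIANALYZE, pooling each separately, through ESTIMATE statements or a filtered LSMEANS `Diffs` table.
- Carry the same model into the tipping-point code.

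No change to the imputation step is needed for this point. The cost is a few lines of sample code. No data, sample size or testing order changes. SAP Section 1 already requires modifications to be documented and approved before unblinding.
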